10.3.2 Secondary Endpoints

Changes in smoke intake and in nicotine intake indexed by salivary anabasine and salivary cotinine levels, assessed for participants still using NRT or EC at end of pregnancy and for 'dual users' or those who have reduced their smoking by 50% or more; 7-day point-prevalence abstinence self-reported at 4 weeks, end of pregnancy and at 3 months post-partum; self-reported prolonged abstinence at end of pregnancy and 3 months post-partum; use of NRT and EC throughout pregnancy; proportion of participants reporting adverse events and serious adverse events in each group; proportion of participants in each group reporting adverse events and serious adverse events for themselves or their infant at 3 months post-partum; birth and maternal outcomes.

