10.5 Objectives and End Points Summary

Primary Objective	Primary Endpoint	Outcome Measures
Efficacy of EC compared to	Abstinence rates in each	Prolonged abstinence at end of
NRT	group at end of	pregnancy from 2 weeks post-
	pregnancy	TQD defined as per Russell
		Standard abstinence criteria,
		biochemically validated
Secondary Objectives	Secondary Endpoints	Outcome Measures
Effects on Smoke and	Change in smoke and	Salivary cotinine and anabasine
Nicotine intake from EC and	nicotine intake from	
NRT users; 'dual users'; and	baseline to end of	
reducers (50% or more)	pregnancy	
Efficacy of EC compared to	Abstinence at 4 weeks	Self-reported point prevalence
NRT	post-TQD, end of	abstinence (not a puff over the
	pregnancy, and 3-	previous week) at 4 weeks post-
	months post-partum.	TQD, at end of pregnancy and at 3
		months post-partum; self-
		reported prolonged abstinence at
		end of pregnancy and at 3-
		months post-partum
Treatment adherence	Use of EC and NRT	Self-reported EC and NRT use
		(number of days used; amount
		and products used; product
		changes)
Safety of EC compared to	Adverse events	Self-reported adverse events and
NRT	throughout the	SAE's
	intervention period and	
	at 3 months post-	SAE's identified at 3-months post-
	partum (for both	partum follow-up calls.
	mother and infant).	
	Birth and maternal	Birth and maternal outcomes:
	outcomes	Birth weight; gestational age; C-
		section delivery; still
		birth/miscarriage/neonatal or
		post-neonatal death; maternal
		death; neonatal intensive care
		admission

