Smoking status; use of EC, NRT and any other stop smoking medications; adverse events. We will also collect birth and maternal outcomes with the prior consent of participants (date of birth, birthweight, gestational age, still births, miscarriage, maternal death, congenital abnormalities, neonatal and post-neonatal deaths, neonatal intensive care admission and delivery by C-section) from hospital records. Participants reporting abstinence from smoking, reduction of cigarette consumption of 50% or more, and those smoking and using NRT or EC, will be asked to provide saliva samples for cotinine and anabasine analysis. Sampling kits will be sent by post together with instructions, and self-addressed envelope for sample return. A visit will be offered if postal samples are not returned. Participants will be provide with £20 for their time in returning the saliva sample. The cut off points for classifying participants as abstainers will be cotinine < 15 ng/ml [42] for those not reporting using any nicotine product and anabasine< 1 ng/ml [43] for those reporting any NRT/EC use.

Three months post-partum phone call

Participants will be contacted to check on any adverse events to themselves or their infant since end of pregnancy, and to record smoking status and product use.

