12.8.4 Follow up Procedures

Participants will be contacted for 2 data collection follow up calls post intervention; one at the end of pregnancy (35 week gestation to ten weeks post-partum) and the other 3 months post-partum. Participants will be sent a text message a few days before the call is due to ask for a suitable time to call. The QM team will attempt telephone contact first. If this is unsuccessful, participants will also be contacted via text, email and letter. There may also be the opportunity for the research team at the local site to see the participant at the clinic or to arrange a home visit. If the participant is agreeable to this, the research team will collect the follow up questions and return the saliva sample.

At three months post-partum, the study team will make 3 telephone attempts to contact the participant to collect further safety and outcome data.

Preventing distress: Many women who miscarry can participate in follow up without upset; however, calls can occasionally be distressing (e.g. relatives answering after maternal death). We will not routinely exclude women who have miscarried from follow up, but the following will minimise potential distress. The co-ordinating trial office will send the local research teams a list of participants to be followed up within the next fortnight; the local research team will be asked to identify anyone they either know to have or whose medical records show them to have experienced an event which might make follow up distressing. The opinions of the local research team will be considered when deciding whether or not to attempt follow up. In addition to this, a text reminder will be sent to all participants the day before their follow up call is due. Participants may then text back if they do not wish to be called. A reminder text will also allow participants to schedule a convenient time for their call. Participants will be able to text back their smoking status if a call is not convenient.

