15.6 Serious Adverse Events that do not require expedited reporting

The following will be considered **expected serious adverse events (SAEs) and will not be reported in an expedited manner** (see section 15.7) but will be recorded.

Events requiring hospital admission (overnight stay) which are related to the underlying pregnancy, these include: recognised pregnancy or postnatal complications, including pre-term delivery, low birth weight, birth injury, infection, thrombosis, haemorrhage, hypertensive disease, instrumental delivery, caesarean section, and antenatal admissions for pregnancy related diseases such as false labour, infection, thrombosis, haemorrhage, hypertensive disease, suspected or confirmed foetal compromise, vaginal bleeding foetal congenital abnormalities, and infant hospital admissions; and incidental hospital admissions for minor, gastrointestinal diseases, respiratory, cardiac, renal skin, psychiatric and neurological problems.

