17.6 Secondary outcome analysis

Secondary and safety outcomes will also be analysed on an intention to treat basis where possible. Binary outcomes including self-reported quit rates at 4 weeks post-quit and at end of pregnancy, and 7-day point-prevalence abstinence will be analysed by logistic regression and continuous outcomes, including birthweight and gestational age by multiple linear regression. In infant outcomes analysis we will allow for clustering in multiple births.

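### As worded, the 3-month safety endpoint is one mother-or-infant proportion per woman, so non-fatal infant events get no comparison of their own

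*Protocol*

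**What the plan says.** Protocol 10.3.2 lists, among the secondary endpoints, the "proportion of participants in each group reporting adverse events and serious adverse events for themselves or their infant at 3 months post-partum". The unit is the participant, who is the mother, and the two people are joined by *or*.

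Other sections describe the same contact differently:

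- **10.5 (summary table).** The endpoint column covers adverse events at 3 months for mother and infant both, without saying whether they are analysed apart. The outcome-measures column ties only serious events to that call: "SAE's identified at 3-months post"-partum.
- **9.0 (flowchart).** The 3-month call collects serious adverse events in mother and baby since delivery, plus smoking status.
- **12.8.1.** "Participants will be contacted to check on any adverse events to themselves or their infant since end of pregnancy", with no restriction to serious events.
- **12.8.4.** "the study team will make 3 telephone attempts to contact the participant to collect further safety and outcome data". No expected response rate is given.
- **17.6.** Safety outcomes are analysed by intention to treat where possible, and "In infant outcomes analysis we will allow for clustering in multiple births".

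Several infant outcomes are named separately. 10.5 lists birth weight, gestational age, stillbirth, miscarriage, neonatal or post-neonatal death, and neonatal intensive care admission. 12.8.1 also takes "congenital abnormalities, neonatal and post-neonatal deaths, neonatal intensive care admission and delivery by C-section) from hospital records".

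**The concern.** A woman counts once under 10.3.2 whether the event was hers, her infant's or both. Mother and infant have different exposures and different background risks. If the arms differ only in infant events, women whose own event already puts them in the numerator contribute nothing to the contrast, and the remaining difference sits on a higher and noisier background rate.

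The unit is also awkward. Twins who each have an event count as one woman, so the allowance for multiple births in 17.6 has nothing to act on in this endpoint.

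What is at stake is narrow but real. Section 15.6 lists infant hospital admissions among the expected serious events that are recorded but not expedited. Apart from neonatal intensive care admission, they belong to no named birth outcome. Among the named endpoints, the 3-month proportion is therefore the only place where a difference between arms in infant admissions after discharge would be compared. Safety is the first secondary objective in 10.2.

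**Working it through.** **Inputs.** From the protocol (17.1): 570 per arm, two-sided alpha 0.05. Assumed, because the protocol gives no maternal or infant event rate: infant rates of 5% and 10% in the two arms; a maternal rate m, equal in both arms, of 5% to 30%; maternal and infant events independent; everyone reached at 3 months; one infant per woman.

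**Step 1: the plan's own figure.** The protocol states no figure for this endpoint, so the formula is checked on the primary endpoint. With p̄ = (p0 + p1)/2,

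power = Φ{ [ |p1 − p0|·√n − 1.96·√(2p̄(1 − p̄)) ] / √(p0(1 − p0) + p1(1 − p1)) }.

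For 8% against 14% with n = 570 this gives 90.0%, and solving for n at 90% gives 570 per arm, 1,140 in total, as stated in 17.1. For 8% against 13.1% it gives 80.1%, against the stated 80%. The formula matches the plan.

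**Step 2: infants alone.** For 5% against 10%: √570 = 23.875 and p̄ = 0.075. The numerator is 0.05 × 23.875 − 1.96 × √0.13875 = 1.194 − 0.730 = 0.464. The denominator is √(0.0475 + 0.0900) = 0.371. Power = Φ(1.25) = 89.4%.

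**Step 3: mother or infant.** With infant rate i, the combined rate is c = 1 − (1 − m)(1 − i), so the difference between arms becomes (1 − m)(i1 − i0).

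| Maternal rate m | Combined rates | Difference (points) | Risk ratio | Power |
|---|---|---|---|---|
| infants alone | 5.0% vs 10.0% | 5.0 | 2.00 | 89.4% |
| 5% | 9.75% vs 14.5% | 4.75 | 1.49 | 69.1% |
| 10% | 14.5% vs 19.0% | 4.5 | 1.31 | 53.0% |
| 20% | 24.0% vs 28.0% | 4.0 | 1.17 | 33.7% |
| 30% | 33.5% vs 37.0% | 3.5 | 1.10 | 23.5% |

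Worked row, m = 10%: numerator 0.045 × 23.875 − 1.96 × √(2 × 0.1675 × 0.8325) = 1.074 − 1.035 = 0.039; denominator √(0.123975 + 0.1539) = 0.527; Φ(0.075) = 53.0%.

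Most of the loss comes from variance. At m = 10% the difference shrinks by a tenth, while its standard error rises from √(0.1375/570) = 0.0155 to √(0.277875/570) = 0.0221.

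**Step 4: incomplete follow-up.** If only 400 per arm were reached (an assumption), power on infants alone is 77%. In the combined measure it is 40%, 25% and 18% at m = 10%, 20% and 30%.

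**The case against.** **The wording may be shorthand.** The same clause joins adverse and serious adverse events with *and*, and nobody would require both in one woman. Section 10.5 speaks of mother and infant both, 17.6 already foresees an infant analysis, and an analysis plan that is not shown may separate the two. This stands in part. But 10.5 does not settle the matter, no section names a separate 3-month infant proportion, and an analysis plan that follows 10.3.2 as written would inherit the combined endpoint. Section 17.6 does not say that infant outcomes are analysed per infant. That is an inference from the allowance for multiple births, and it is why the sections need reconciling rather than being a flat contradiction.

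**Infant safety is protected elsewhere.** A reader might infer that the endpoint hides infant harm in general. The documents do not support that. Fatal outcomes, birth weight, gestational age and neonatal intensive care admission are separate endpoints, and congenital abnormalities come from hospital records. Section 15.7 lists reportable serious events for baby and mother separately. The monitoring committee includes a neonatologist (15.11) and sees serious events unblinded (27.0). This objection stands and confines the point to non-fatal events outside that list. Committee review of individual events does not, however, replace a reported comparison between arms.

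**Maternal events may not be common at 3 months.** A reader might infer from 15.6 that they are, since it names "haemorrhage, hypertensive disease, instrumental delivery, caesarean section, and antenatal admissions for pregnancy related diseases". It gives no rates, and antenatal admissions fall outside the period that the 3-month call covers. This stands: the size of the loss is unknown. Its direction under equal maternal rates is not, since even a 5% maternal rate costs about 20 points of power (89.4 − 69.1) in the example.

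**A combined measure can gain power** if maternal events differ in the same direction. This also stands, so the result is limited to a difference confined to infants. The trial claims no power for any safety endpoint.

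**Conclusion.** The point holds in a limited form and is a cheap improvement. As written, 10.3.2 makes the 3-month safety endpoint one proportion per woman with an event in mother or infant, and no infant proportion stands beside it. For non-fatal infant events outside the birth-outcome list, chiefly admissions after discharge, this lowers sensitivity to a difference confined to infants. In the example, power falls from 89% to between 69% and 24% across maternal rates of 5% to 30%. Those figures rest on assumed event rates, independence, equal maternal rates in both arms and full follow-up. They illustrate the mechanism and do not forecast this trial.

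Separately, the sections disagree on what is counted at 3 months: adverse and serious events in 10.3.2, adverse events in 12.8.1, serious events only in 9.0 and in the outcome-measures column of 10.5.

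**What to change.** In 10.3.2 and 10.5, replace the single 3-month endpoint with two:

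- (a) the proportion of mothers with an adverse event, and with a serious adverse event;
- (b) the proportion of infants with an adverse event, and with a serious adverse event, with liveborn infants as the denominator and allowance for clustering in multiple births as in 17.6.

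Keep the mother-or-infant proportion, if wanted, as a descriptive figure only. State once whether the 3-month call counts all adverse events or only serious ones, and align 9.0, 10.3.2, 10.5 and 12.8.1 with that.

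The cost is a wording change and a little more tabulation. The call already asks about mother and infant, so no new data collection, contact or sample size is needed.

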10.4 Exploratory or Tertiary endpoints/outcomes

Inclusion of longer-term outcomes:

We understand the need to plan for potential longer term follow up if an unexpected difference in birth outcomes emerges. Should this happen, we would apply (separately from this application) for additional funding to examine longer term outcomes for both mother and child but to prepare for this, we will undertake some early steps 'up front'. This will include ensuring that the informed consent allows us to use NHS mechanisms for finding out people's addresses or to use NHS numbers for women's and infant's follow up. Having adequate initial consent will ensure that we do not have to re-consent participants.

10.5 Objectives and End Points Summary

Primary Objective	Primary Endpoint	Outcome Measures
Efficacy of EC compared to	Abstinence rates in each	Prolonged abstinence at end of
NRT	group at end of	pregnancy from 2 weeks post-
	pregnancy	TQD defined as per Russell
		Standard abstinence criteria,
		biochemically validated
Secondary Objectives	Secondary Endpoints	Outcome Measures
Effects on Smoke and	Change in smoke and	Salivary cotinine and anabasine
Nicotine intake from EC and	nicotine intake from	
NRT users; 'dual users'; and	baseline to end of	
reducers (50% or more)	pregnancy	
Efficacy of EC compared to	Abstinence at 4 weeks	Self-reported point prevalence
NRT	post-TQD, end of	abstinence (not a puff over the
	pregnancy, and 3-	previous week) at 4 weeks post-
	months post-partum.	TQD, at end of pregnancy and at 3
		months post-partum; self-
		reported prolonged abstinence at
		end of pregnancy and at 3-
		months post-partum
Treatment adherence	Use of EC and NRT	Self-reported EC and NRT use
		(number of days used; amount
		and products used; product
		changes)
Safety of EC compared to	Adverse events	Self-reported adverse events and
NRT	throughout the	SAE's
	intervention period and	
	at 3 months post-	SAE's identified at 3-months post-
	partum (for both	partum follow-up calls.
	mother and infant).	
	Birth and maternal	Birth and maternal outcomes:
	outcomes	Birth weight; gestational age; C-
		section delivery; still
		birth/miscarriage/neonatal or
		post-neonatal death; maternal
		death; neonatal intensive care
		admission

10.6 Trial Design

A pragmatic multi-centre RCT comparing behavioural support and nicotine patch NRT (usual care) with the same behavioural support accompanied instead by EC.

Duration of participation: The length of duration in the study will vary depending on what stage in their pregnancy the participant is randomised into the trial. The maximum duration in the study will be 10 months (from earliest point of recruitment at 12 weeks gestation to the final follow up at 3 months post-partum, including an additional month to allow follow-up on non-responders). The minimum length of duration will be 7 months.

Number of visits: Participants will attend one session with the research team. Other study contact will be via phone apart from cases where the research team are able to collect the saliva sample in person.

10.7 Study Setting

Participants will be recruited by maternity services at sites across England, and by Stop Smoking Service in Scotland. We plan to include at least 23 recruiting sites across England and 1 site in Scotland, and have a further 6 sites in England, and 2 sites in Scotland as reserve sites, in case of slow recruitment rates. Queen Mary University of London is a non-recruiting, Non NHS Site, acting as the coordinating centre and performing intervention delivery, data collection and follow up telephone calls.

In England, Clinical Research Networks (CLRN) research midwives (RM) and routine care staff will recruit potential participants. In some sites RM may not be routinely available, but other relevant staff (such as clinical trial associates or research nurses) would be trained to carry out the research procedures. Those not eligible to take part in the study but interested in obtaining help with stopping smoking will be referred to local stop smoking services as per standard practice.

11.0 Eligibility Criteria

11.1 Inclusion Criteria

- Aged 18 years or over
- Daily smokers
- 12 to 24 weeks pregnant
- Wants help with stopping smoking
- Willing to be randomised to use either NRT or EC (to avoid selective drop-out and contamination)
- Wiling to receive 6 weekly support calls over the phone plus two follow-up calls
- Speaks and reads English to a level that permits data collection via the telephone

11.2 Exclusion Criteria

- Known allergic reaction to nicotine skin patches (a contraindication for patch use)
- Current daily use of NRT or EC
- Taking part in another interventional trial
- Serious medical problem or high-risk pregnancy at time of initial consent* (to avoid problems with followup and data collection)

12.0 Trial Procedures

^{*} Note: we will not automatically withdraw participants from the study if their pregnancy becomes high-risk during the trial as this could bias the evaluation of safety outcomes.

12.1 Recruitment

Dependant on the Site setup, participants will be recruited by research midwives (RMs) or other appropriately trained staff (such as specialist pregnancy stop smoking service (SSS). The RM or SSS advisor would also take consent and conduct the baseline and randomisation visit and obtain birth and maternal outcomes data as required.

12.2 Participant identification

The usual care team will identify potential participants from patient records and send PIS and invitation letters alongside 12 or 20 week scan appointment letters; contact the participants via telephone, letter, email or text; or the research team may ask women to complete a screening questionnaire when they attend hospital for their ultrasound scan appointments. Community midwives who see pregnant smokers at booking appointments or at other routine care appointments will also be briefed to refer any pregnant smokers interested in the study to the research team. Posters advertising the study will also be placed within the sites' antenatal clinics, or in Scotland, at the participating SSS.

Potential participants identified by hospital records will be pre-screened to check that they meet some of the eligibility criteria, e.g. by checking they are 18 years of age, between 12-24 weeks pregnant and daily smokers. If offered the study by phone or in person, pre-screening will encompass all eligibility criteria.

Women identified as potential participants will receive the study information sheet (PIS) (depending on the recruitment route either in person or in the post/email) and an invitation to attend a screening and randomisation session or, where appropriate, a home visit. Participants will be given sufficient time to consider the PIS. A screening log will be kept by staff of how many people have been offered the study.

Confidentiality will be maintained at all times as all women in England and Scotland who are identified as smokers at their booking appointments are normally routinely offered stop-smoking support, either in-house or referred to a local stop-smoking service. No one outside of the direct care team will have access to identifiable personal information of any potential participants prior to consent. In some sites, the research team may be a part of the usual care team; where they are not, only the direct care team will access personal data and invite potential participants to the study.

12.3 Informed Consent Procedures

12.3.1 Responsibility for obtaining consent

The research team will be delegated by the local PI to obtain consent from participants. Local PI's will confirm eligibility and sign off consent forms after randomisation, but prior to dispensing of any study products. They will be blind to randomisation to avoid a possible bias. Staff taking consent will be trained in study consenting procedures and GCP (CTIMP) trained, this will be recorded in a Study training log within the ISF.

12.3.2 Consent Considerations

The right of a participant to refuse participation without giving reasons will be respected.

The participant will remain free to withdraw at any time from the trial without giving reasons and without prejudicing his/her further treatment and will be provided with a contact point where she may obtain further information about the trial. Where a participant is required to re-consent, for example if during the trial new Research Safety Information becomes available, or following an amendment that affects the patient, or new information needs to be provided to a participant, it will be the responsibility of the CI and local PI to ensure this is done in a timely manner.

